2.3.1 Risk Assessment

A standard battery of toxicology studies was conducted with TB006. The pivotal safety assessment was a 1 month GLP toxicology study in cynomolgus monkeys. Doses ranged from 10 to 200 mg/kg, and evaluation included clinical and laboratory observations, a 5 week recovery period, and full histopathology. No treatment related adverse findings were observed. Mild lymphoid hyperplasia occurred in males at the 10, 100, and 200 mg/kg dose levels, but based on mild severity, lack of dose dependency and historical test facility data from similar studies in cynomolgus monkeys, this finding was considered a species specific mild, reactive immune response and not an adverse toxicological finding. It is likely an immunogenicity reaction. No other findings were observed in this or any of the other toxicology studies.

TB006 is a first in class monoclonal antibody, therefore there are no known class adverse effects or risks to report from clinical studies. In general, risks associated with other monoclonal antibodies include allergic reactions such as hives or itching, flu like symptoms such as chills, fatigue, fever, and muscle aches and pains, nausea and vomiting, skin rashes and decreases in blood pressure. These effects have not been observed in preclinical studies to date. Other marketed IgG4 humanized monoclonal antibodies, such as natalizumab, eculizumab, and pembrolizumab, are used clinically. These antibodies largely target the immune system. There appears to be a spectrum of target-related negative effects when the total antibody dose gets too high. This pattern is not evident with TB006 in the preclinical toxicology profile, but will be closely observed in Phase 1 studies.

When performed correctly and according to industry standards, venipuncture complications are rare. However, even when properly performed, complications can include fainting, dizziness, hematoma, nerve injury, and arterial puncture or laceration. Blood draws and administration of the IV infusion in this study will be performed adequately trained medical staff to minimize any risk to patients.

Risks associated with a lumbar puncture can include headache, pain or numbness, bleeding, infection, puncture pain, and herniation. The lumbar puncture procedure will be performed by medical staff experienced with the technique and using aseptic techniques to minimize any risk to patients.

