6.2.1 Dose Escalation and Stopping Considerations

While concrete dose escalation stopping criteria will not be included, the following variables (at a minimum) will be taken into account by the SRC at the protocol-specified time points for these decisions, and when events arise during the course of study treatment:

- Number and frequency of treatment-related AEs characterized as moderate or severe in severity
- Number and frequency of treatment-related SAEs
- Discontinuation due to AEs
- Emergent cardiovascular events, such as QTc increases or vital sign changes
- Liver function enzyme increases

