- Grade 3: Severe or medically significant but not immediately life-threatening; hospitalization or prolongation of hospitalization indicated; disabling; limiting self-care ADL (eg, bathing, dressing and undressing, feeding self, using the toilet, taking medications).
 - An AE that is assessed as severe should not be confused with an SAE. Severe is a category utilized for rating the severity of an event; and both AEs and SAEs can be assessed as severe. An event is defined as 'serious' when it meets at least 1 of the predefined outcomes as described in the definition of an SAE, NOT when it is rated as severe.
- Grade 4: Life-threatening consequences; urgent intervention indicated.
- Grade 5: Death related to AE.

Assessment of Causality

- The investigator is obligated to assess the relationship between study drug and each occurrence of each AE/SAE.
- A "reasonable possibility" of a relationship conveys that there are facts, evidence, and/or
 arguments to suggest a causal relationship, rather than that a relationship cannot be ruled
 out.
- The investigator will use clinical judgment to determine the relationship.
- Alternative causes, such as underlying disease(s), concomitant therapy, and other risk
 factors, as well as the temporal relationship of the event to study drug administration, will
 be considered and investigated.
- The investigator will also consult the IB in his/her assessment.
- For each AE/SAE, the investigator must document in the medical notes that he/she has reviewed the AE/SAE and has provided an assessment of causality.
- There may be situations in which an SAE has occurred and the investigator has minimal
 information to include in the initial report. However, it is very important that the
 investigator always makes an assessment of causality for every event before the initial
 transmission of the SAE data.

Protocol TB006AD2102

Protocol Date and Version: 15 Oct 2021; v 3.0

 The investigator may change his/her opinion of causality in light of follow-up information and send an SAE follow-up report with the updated causality assessment.

- The causality assessment is one of the criteria used when determining regulatory reporting requirements.
- Causality assessments are defined below:
 - Causality assessments that indicate the event is "Not Drug Related":
 - Unrelated: The event is related to an etiology other than the study drug administration (the alternative etiology must be documented in the patient's medical record).

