 - Unlikely: The event is unlikely to be related to the study drug and likely to be related to factors other than study drug.
 - Causality assessments that indicate the event is "Drug Related":
 - Possible: There is an association between the event and the administration of study drug and there is a plausible mechanism for the event to be related to the study drug; but there may also be alternative etiology, such as characteristics of the patient's clinical status or underlying disease.
 - Probable: There is an association between the event and the administration of study drug and there is a plausible mechanism for the event to be related to the study drug, and the event could not be reasonably explained by known characteristics of the patient's clinical status or an alternative etiology is not apparent.
 - Definite: There is an association between the event and the administration of study
 drug and there is a plausible mechanism for the event to be related to the study drug
 and causes other than the study drug have been ruled out and/or the event re-appeared
 on re-exposure to the study drug.

Follow-up of AEs and SAEs

- The investigator is obligated to perform or arrange for the conduct of supplemental
 measurements and/or evaluations as medically indicated or as requested to elucidate
 the nature and/or causality of the AE or SAE as fully as possible. This may include
 additional laboratory tests or investigations, histopathological examinations, or
 consultation with other health care professionals.
- If a patient dies during participation in the study or during a recognized follow-up period, the investigator will provide the sponsor with a copy of any post-mortem findings including histopathology.
- New or updated information will be recorded in the originally completed CRF.
- The investigator will submit any updated SAE data to the sponsor within 24 hours of receipt of the information.

Protocol TB006AD2102

Protocol Date and Version: 15 Oct 2021; v 3.0

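### All three drug-related causality categories require a plausible mechanism, so an event that follows dosing with no mechanism and no other cause identified fits none of the five definitions

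*Protocol*

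**What the plan says.** Protocol 10.2.3 (Assessment of Causality) obliges the investigator to assess every AE and SAE and defines five categories. None of them is for unknown or not assessable.

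Three categories count as drug related:
- The lowest is worded "Possible: There is an association between the event and the administration of study drug and there is a plausible mechanism for the event", meaning a way in which the drug could have caused it. Another etiology may also be present.
- The next is worded "Probable: There is an association between the event and the administration of study drug and there is a plausible mechanism for the event", in the same sense, with the added condition that either the patient's known characteristics do not reasonably explain the event or no other etiology is apparent.
- Definite repeats both requirements, association and mechanism, with a further element: "and causes other than the study drug have been ruled out and/or the event re-appeared" when the drug was given again.

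Two count as not drug related. Unrelated needs a different etiology, documented in the medical record. The other is "Unlikely: The event is unlikely to be related to the study drug and likely to be related to factors other than study drug".

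Earlier in the same section is a general standard: a reasonable possibility "conveys that there are facts, evidence, and/or" arguments that suggest a causal link. Being unable to exclude a link is expressly not enough. The investigator is to use clinical judgment and to weigh alternative causes, the timing relative to dosing and the Investigator's Brochure. Mechanism is not mentioned there.

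On the product, Protocol 2.3.1 says: "TB006 is a first in class monoclonal antibody, therefore there are no known class adverse effects or risks to report from clinical studies".

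**The concern.** The general standard and the category definitions set different tests. An investigator who follows the general standard can call an event a reasonable possibility on timing and the absence of another explanation. An investigator who follows the definitions cannot, unless a plausible mechanism can also be named. The recorded category comes from the definitions.

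The condition works in one direction. It can take an event out of the related group but cannot put one in. It bears most on toxicity nobody has yet explained, and finding such toxicity is one purpose of Part 1 with a first-in-class antibody.

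Relatedness is used in several places:
- **Dose escalation.** Two of the five minimum variables in Protocol 6.2.1 depend on it: "Number and frequency of treatment-related AEs characterized as moderate or severe in severity", and the corresponding count of treatment-related SAEs.
- **Disease-related events.** Under Protocol 8.3.5, a fall, psychosis or worsening of AD must be reported as an SAE if the investigator sees a reasonable possibility of a drug relationship. That exception uses the general standard's term, so the two halves of 10.2.3 can give different answers for the same event.
- **Regulatory reporting.** Protocol 10.2.3 makes causality one input.
- **Related-AE tables.** SAP 12.1 takes the related flag from the investigator's eCRF entry.

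SAP 9.6 treats a relationship as related only when it is missing. An event recorded as Unlikely is left as it is.

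**Working it through.** The check is mainly one of logic. The plan gives no figure to reproduce.

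**Step 1. Define the test case.** A = association with dosing: yes. M = plausible mechanism: none identified. E = alternative cause: none found.

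**Step 2. Test the case against each definition in Protocol 10.2.3.**

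| Category | What it needs | Result |
|---|---|---|
| Possible | A and M | Fails on M |
| Probable | A and M, plus no reasonable or apparent other explanation | Fails on M, although the last element is met |
| Definite | A and M, plus other causes excluded and/or recurrence on re-exposure | Fails on M |
| Unrelated | A documented E | Fails, nothing to document |
| Unlikely | Other factors the likely cause | Fails, no such factor |

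The case fits 0 of 5. The missing mechanism alone closes 3 of 3 related categories.

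**Step 3. Compare with the general standard.** It asks for facts, evidence and/or arguments, and names timing and alternative causes as things to weigh. A clear association with nothing else to explain the event is evidence of that kind. The case can therefore meet the general standard while being barred from every category that would record it as related.

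**Step 4. Repeat with a positive re-exposure.** Suppose the event also recurs on re-exposure and other causes are excluded, still with no mechanism. Definite remains closed because its first clause needs M. The problem is therefore present in all three related categories.

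**Step 5. Illustrate the size, with assumed events.** A Part 1 group has 8 patients, 6 on TB006 and 2 on placebo (Protocol 6.4.1), and the safety review committee is blinded (Protocol 4.1 and 9.6). It would therefore see pooled counts out of 8. Assume two patients have a moderate event of the Step 1 type.
- Recorded as related: 2/8 = 25%. Exact 95% limits solve P(X ≥ 2 | 8, p) = 0.025, giving p ≈ 3%, and P(X ≤ 2 | 8, p) = 0.025, giving p ≈ 65%.
- Recorded as not related: 0/8.

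In general, k such patients change the related count from k/8 to 0/8: no change at k = 0, 12.5% to 0 at k = 1, 25% to 0 at k = 2. The documents give no basis for choosing k.

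**The case against.** The strongest reply is that the affected set may be close to empty. The protocol asks for a plausible mechanism, which is less than a recognised one. Protocol 2.2.2 describes galectins in many tissues, 2.3.1 lists general antibody reactions, and 4.3 anticipates immune-mediated effects, so an investigator will often be able to argue a mechanism. Clinical judgment is expressly allowed. This stands, and it limits the size of the problem. It does not remove the conflict between the two tests.

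A second reply concerns where such events go. A reader might infer that the protocol sends them to the not-related group. The documents do not say so. On a literal reading Unrelated and Unlikely fail too, so the text is silent. Filing as Unlikely is a reasonable guess, because an assessment is compulsory and Unlikely needs no documented alternative, but it remains a guess.

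A third reply is that other safeguards do not depend on relatedness. Three of the five variables in Protocol 6.2.1 (discontinuations due to AEs, cardiovascular events, liver enzymes) do not use it, and the list is a minimum with no fixed stopping criteria. All SAEs reach the sponsor within 24 hours whatever their cause (Protocol 8.3.1). SAP 12.1 tabulates all treatment-emergent AEs by term and grade. This stands as well: one input is weakened and the rest remain.

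A fourth reply is that the general standard is not wholly permissive, since failure to exclude a link is insufficient. That is correct, and the remedy has to respect it.

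**Conclusion.** The point holds as an internal inconsistency with a one-way effect. As written, an event associated with dosing but with no plausible mechanism and no alternative cause cannot be recorded as drug related and fits none of the five definitions, although it can meet the section's own general standard.

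The size cannot be derived from the documents. It is zero if investigators can argue a mechanism for every AE, and rises with each one they cannot. The 0/8 against 2/8 contrast rests on two assumed events, and on their being recorded as not related.

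Two stronger readings go too far. First-in-class status means that no class effects are known from clinical studies. It does not mean that no mechanism can be proposed. Nor do the documents support saying that the committee would miss a toxicity signal, since it reviews safety data beyond the related events.

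**What to change.** Amend Protocol 10.2.3 in two ways:
1. In Possible, Probable and Definite, make a plausible mechanism evidence that supports a relationship, no longer a necessary condition. Changing Possible alone is not enough, because an unexplained event that recurs on re-exposure would then be capped at Possible.
2. State that an event with a reasonable temporal association and no more likely alternative cause is at least Possible.

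The test case is then at least Possible, Probable is open to it, and a positive re-exposure with other causes excluded can reach Definite. Because a reasonable association is positive evidence, the change remains compatible with the rule that mere non-exclusion is insufficient. The amendment should say what counts as reasonable: AEs are collected to Day 104 and Protocol 4.3 expects a half-life longer than the 10 to 12 days seen in monkeys, so a loose reading could take in many events.

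This does not make the five categories exhaustive. An event with no association and no identified cause would still have no exact place, and one added sentence could assign it.

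The cost is a short amendment and a site training note, with no new data. The drawback is somewhat more events called related. They would arise in both blinded arms, so the comparison with placebo can still show an excess on TB006.

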10.2.4 Reporting of Serious Adverse Events

SAE Reporting to via an Electronic Data Collection Tool

- The primary mechanism for reporting an SAE will be the electronic data collection tool.
- If the electronic system is unavailable, then the site will use the paper SAE data collection tool in order to report the event within 24 hours.
- The site will enter the SAE data into the electronic system as soon as it becomes available.
- After the study is completed at a given site, the electronic data collection tool will be taken off-line to prevent the entry of new data or changes to existing data.
- If a site receives a report of a new SAE from a study patient or receives updated data
 on a previously reported SAE after the electronic data collection tool has been taken
 off-line, then the site can report this information on a paper SAE form or to the
 Medical/Scientific Monitor by telephone.
- Contacts for SAE reporting are noted below.

10.2.5 National Cancer Institute Common Terminology Criteria for Adverse Events, Version 5.0

The NCI CTCAE is a descriptive terminology which can be utilized for AE reporting. A grading (severity) scale is provided for each AE term.

Grade refers to the severity of the AE. The CTCAE displays Grades 1 through 5 with unique clinical descriptions of severity for each AE based on this general guideline:

- Grade 1: Mild; asymptomatic or mild symptoms; clinical or diagnostic observations only; intervention not indicated.
- Grade 2: Moderate; minimal, local or noninvasive intervention indicated; limiting age-appropriate instrumental ADL*.
- Grade 3: Severe or medically significant but not immediately life-threatening; hospitalization or prolongation of hospitalization indicated; disabling; limiting self-care ADL**.
- Grade 4: Life-threatening consequences; urgent intervention indicated.
- Grade 5: Death related to AE.

Published date of version 5.0: 27 Nov 2017, available here:

^{*}Instrumental ADL refer to preparing meals, shopping for groceries or clothes, using the telephone, managing money, etc.

^{**}Self-care ADL refer to bathing, dressing and undressing, feeding self, using the toilet, taking medications, and not bedridden.

Protocol TB006AD2102

Protocol Date and Version: 15 Oct 2021; v 3.0

 $https://ctep.cancer.gov/protocolDevelopment/electronic_applications/docs/CTCAE_v5_Quick_R\\ eference_5x7.pdf$

from:

https://ctep.cancer.gov/protocolDevelopment/electronic_applications/ctc.htm#ctc_50

Protocol TB006AD2102

Protocol Date and Version: 15 Oct 2021; v 3.0

10.3 Appendix 3: Liver Safety: Suggested Actions and Follow-up Assessments

Phase 1 liver chemistry stopping criteria define liver injury, evaluate liver event etiology, and are considered in dose escalation decisions.

Table 9. Phase 1 Liver Chemistry Stopping Criteria and Follow-up Assessments

Liver Chemistry Stopping Criteria			
ALT-absolute	Alanine aminotransferase (ALT) \geq 3 × upper limit of normal (ULN) If ALT \geq 3 × ULN AND bilirubin \geq 2 × ULN (> 35% direct bilirubin) or international normalized ratio (INR) > 1.5, report as a serious adverse event (SAE) ^{a,b}		
	See additional actions and follow-up assessments below		
	Required Actions and Follow-up Assessments		
Actions		Follow-Up Assessments	
 Report the ev 24 hours Complete the (CRF), and co collection too criteria for an Perform liver assessments Monitor the pabnormalities 	discontinue study drug ent to the sponsor within liver event case report form complete an SAE data il if the event also met the SAE ^b function follow-up catient until liver function test resolve, stabilize, or return ee MONITORING)	 Viral hepatitis serology^c Obtain INR and recheck with each liver chemistry assessment until the transaminases values show downward trend Serum creatine phosphokinase (CPK) and lactate dehydrogenase (LDH) Fractionate bilirubin, if total bilirubin ≥ 2 × ULN Complete blood count with differential to assess eosinophilia Record the appearance or worsening of 	
 MONITORING: If ALT ≥ 3 × ULN AND bilirubin ≥ 2 × ULN or INR > 1.5 Repeat liver function tests (include ALT, aspartate transaminase [AST], alkaline phosphatase, bilirubin and INR) and perform liver function follow-up assessments within 24 hours. Monitor patient twice weekly until liver function test abnormalities resolve, stabilize, or return to baseline. 		 Record the appearance of worsening of clinical symptoms of liver injury, or hypersensitivity, on the AE CRF Record use of concomitant medications (including acetaminophen, herbal remedies, and other over-the-counter medications) on the concomitant medications CRF Record alcohol use on the liver event alcohol intake CRF If ALT ≥ 3 × ULN AND bilirubin ≥ 2 × ULN or INR > 1.5: 	

Protocol TB006AD2102

Protocol Date and Version: 15 Oct 2021; v 3.0

 A specialist or hepatology consultation is recommended.

If ALT \geq 3 × ULN AND bilirubin < 2 × ULN and INR \leq 1.5:

- Repeat liver function tests (include ALT, AST, alkaline phosphatase, bilirubin and INR) and perform liver function follow-up assessments within 24 to 72 hours
- Monitor patients weekly until liver function abnormalities resolve, stabilize, or return to baseline
- Anti-nuclear antibody, anti-smooth muscle antibody, Type 1 anti-liver kidney microsomal antibodies, and quantitative total immunoglobulin G (IgG) or gamma globulins
- Serum acetaminophen adduct high performance liquid chromatography assay (quantifies potential acetaminophen contribution to liver injury in patients with definite or likely acetaminophen use in the preceding week [James et al, 2009])
- Liver imaging (ultrasound, magnetic resonance, or computerized tomography) and/or liver biopsy to evaluate liver disease; complete liver imaging and/or liver biopsy CRFs
- a Serum bilirubin fractionation should be performed if testing is available. If serum bilirubin fractionation is not immediately available, discontinue study drug if $ALT \ge 3 \times ULN$ and bilirubin $\ge 2 \times ULN$. Additionally, if serum bilirubin fractionation testing is unavailable, **record the absence/presence of detectable urinary bilirubin on dipstick** which is indicative of direct bilirubin elevations suggesting liver injury.
- b All events of ALT ≥ 3 × ULN and bilirubin ≥ 2 × ULN (> 35% direct bilirubin) or ALT ≥ 3 × ULN and INR > 1.5 may indicate severe liver injury (possible 'Hy's Law') and must be reported as an SAE (excluding studies of hepatic impairment or cirrhosis). The INR stated threshold value will not apply to patients receiving anticoagulants.
- c Includes: Hepatitis A immunoglobulin M (IgM) antibody; hepatitis B surface antigen and hepatitis B core antibody; hepatitis C RNA; cytomegalovirus IgM antibody; Epstein-Barr viral capsid antigen IgM antibody (or if unavailable, heterophile antibody or monospot testing); and hepatitis E IgM antibody.

Protocol TB006AD2102

Protocol Date and Version: 15 Oct 2021; v 3.0

A patient who met liver chemistry stopping criteria cannot restart study drug unless all of the following conditions are met:

• TrueBinding Inc. approval is granted (as described below)

- Institutional Review Board/Independent Ethics Committee (IRB/IEC) approval is obtained
- Separate ICF for study drug restart/rechallenge is signed by the patient

If TrueBinding Inc. approval to restart/rechallenge the patient with study drug **is not granted**, then the patient must permanently discontinue study drug and may continue in the study for protocol-specified follow-up assessments.

